13. DATA ANALYSIS

Primary Outcome: The primary outcome will be 7-day point prevalence smoking abstinence at 18 months, defined as self-report of 7 days of not smoking, confirmed by expired CO <8ppm with a Bedfont Smokerlyzer II.^{148,153,218 182} Biochemical verification with available urine cotinine (if not on NRT) and/or anabasine will be used as needed to verify self-reported abstinence, particularly if the validity of CO is expected to be low (e.g. COPD or difficulty forming an adequate seal on the smokerlyzer); and if CO is greater than 8 as this could be from second hand smoke or smoked cannabis.¹⁴⁸⁻¹⁵⁰

7-day smoking abstinence at 6,12 and 15 mo. are secondary outcomes.

Other Secondary outcomes focus on AHA metrics for health risk behaviors²⁰² and include: a) continuous abstinence with 1) % continually abstinent over 3 mo. (based on self-reports of abstinence since last visit, using timeline follow-back²¹⁹, and biochemical verification at 15 and 18 month visits), 2) total days abstinent in the study with the same method, b) Weight and BMI; c) Physical fitness with 6-minute walk;¹⁵⁴⁻¹⁵⁶ and d) Healthy diet.¹⁶⁰ We will assess 10-year probability of a CVD event with the global Framingham Risk Score (FRS) incorporating smoking, total and HDL-cholesterol, systolic blood pressure and diabetes mellitus.²²⁰ Others include: health status (SF-12)¹⁶²; Quality of life (Euroqol);¹⁶³⁻¹⁶⁵ psychiatric symptoms (BPRS);¹⁷⁰ ED use and hospitalizations.

We will also examine the difference of mean CO change over time between intervention arms, and, among continuing cigarette smokers, change of mean number of cigarettes smoked per day over time between intervention arms.

For the primary outcome, we will also perform sensitivity analyses using expired CO<6ppm for abstinent confirmation, as this cutpoint has become more acceptable during the time the trial has been implemented.¹⁵⁰ The outcome using this alternative definition will be modeled in the same fashion.

Our recruitment goal is 220 participants will be recruited from 2 community mental health organizations, enrolled, and randomized in equal allocation to active intervention (Group B) and control (Group A), stratified

Protocol: Trial of Integrated Smoking Cessation, Exercise and Weight Management in SMI

by site and by willingness to set a quit date within 30 days. The enrollment goal is 50% willing to quit in 30 days. Formal assessments are at baseline, 6, 12, 15 and 18 months. Primary analyses will utilize smoking cessation evaluations at 6, 12, 15 and 18 mo. and be conducted under the intention to treat principle.²²¹ The primary outcome is at 18 mo.

Core analytic model: GEE based logistic regression modeling will be conducted using SAS Proc Genmod (or the Stata or R-equivalents) with a logit link and a within-individual, unstructured working correlation model. The primary outcome of smoking cessation at 18 months will be modeled together with the secondary outcomes of smoking cessation at 6, 12 and 15 months.

Let Y_{ijk} denote the binary primary outcome of smoking cessation for the i^{th} participant at the j^{th} visit ($j = 1, 2, \text{ or } 3$), corresponding to the 6-, 12- and 18-month visits), in the k^{th} treatment group ($k = 0 \text{ or } 1$ corresponding to intervention groups A and B). X_{ik} is a vector of pre-randomization covariates (which will include study site indicators). The mean model for the longitudinal data structure of the primary analysis is:

$$\text{logit}\{E(Y_{ijk})\} = \text{logit}\{P_{jk}\} = X_{ik}\eta + \alpha_j + \beta_j \times k \quad (1)$$

so that β_3 represents the adjusted log odds ratio of smoking cessation rate in the intervention vs. the control group at the 18-month visit. Although this mean model could be implemented through a random effects (mixed effects) model in GlimMix, the population-level interpretation of the estimated odds ratios changes with the magnitude of the random effect. For ease of interpretation, we will estimate our primary mean model through the GEE approach in GenMod with resultant estimates representing population average odds ratios.

Although model (1) will support our principal analyses, there is an attractive, transition model alternative. A first-order, autoregressive transition model is a useful adjunct to (1). Note for each participant the outcome is a binary time series that can be analyzed via a series of linked, 2×2 tables (rows are values at visit $(j-1)$, columns at visit j , where visit 0 is baseline), with transitions modeled by logistic regression with treatment effects and, if desired, other covariates. This model could be used to characterize probability of successful abstinence at 12-months among those who were still smokers at 6-months, and at 18-months among those who were smokers at 12-months. Similarly we could estimate relapse rate at a given visit among quitters at the previous visit.

Missing data: Based on our experience, we anticipate less than 10% of follow-up data will be missing.¹²⁵ Prevention is far superior to statistical treatments; every effort will be made to collect data on all randomized. We will use two approaches to missing data. First, in smoking cessation trials, conventionally, those missing smoking data are assumed to be smoking, and we will use this method to be comparable to the field.

^{203,204,222,223} Second, we will perform analyses on the assumption that data is missing at random (MAR). The underlying missing data process determines the biasing effects of missing data and structures valid analytic strategies.²²⁴ If the probability of a potential observation being missing depends on what has, but not on what has not been observed, termed MAR, then estimates based on an appropriate analytic model (both the mean and error structure) for the observed data will not be biased. A valid model for the observed data allows the missing data process to be ignored. If missing is informative, meaning that the probability of an observation being missing depends on the value of that observation after accounting for all the observed data, then bias cannot be avoided by modeling the observed data alone, and the impact should be evaluated using sensitivity analysis. Given that MAR is not a testable hypothesis, we will perform sensitivity analyses to evaluate the robustness of MAR results with multiple imputation using a model derived from our analytical model under MAR, maintaining the covariance structure and modifying the imputation mean according to informative missing data scenarios.

Secondary Analyses (Secondary Aims 1-2): The odds ratio of maintaining continuous abstinence over 15 to 18 months months will be modeled using logistic regression. To evaluate between group difference in change for secondary continuous outcomes such as continuous smoking abstinence (number of days abstinent), weight, 6-minute walk test, global FRS, and psychiatric symptoms (BPRS), we will use linear mixed models employing visit by intervention interaction terms in the mean model and unstructured correlation in the covariance model to estimate intervention effects over time. Outcomes will be log-transformed as appropriate. Emergency department visits and hospitalizations over the three 6-month periods (0-6, 6-12, 12-18 months) will be modeled using mixed effect Poisson regression. All these analyses will be conducted under intention to treat principles. Covariates such as study site and set quit date indicators and other variables associated with

Protocol: Trial of Integrated Smoking Cessation, Exercise and Weight Management in SMI

presence of missing data will be included in the mean model as appropriate.

We will also explore the difference of mean CO change over time between intervention arms, and, among continuing cigarette smokers, change of mean number of cigarettes smoked per day over time between intervention arms using mixed effects regression modeling approach in a similar fashion. For the first exploratory analysis, we will use all patients in the analysis. In the second analysis, we will determine if patients who continue to smoke, smoke less. In this analysis, we will include only patients who are not abstinent. We will use the pattern mixture approach by examining patients in separate groups according to their pattern of missing data to better understand the probability of missing based on patterns of the observed data to inform proper modeling and sensitivity analyses addressing potential informative missing mechanism.

Exploratory Analyses: (Aim 3) We will explore for the potential of treatment effect differential between the participants who are ready to set a quit date within 30 days at baseline and those who are not. This analysis will be conducted under the intention to treat principle and will involve stratified analysis or statistical modeling invoking an interaction term between the status of setting the quit date and the parameter capturing the intervention effect. The trial is not powered to detect such an interaction but the result should be informative for future intervention and trial design. For other subgroups of interest defined at baseline (e.g., psychiatric diagnosis), we will adopt a similar analytic approach. In addition to analyses that preserve the intention to treat principle, we will perform informative exploratory analyses based on subgroups defined post-randomization to characterize aspects of the intervention that may be related to improved abstinence, weight, fitness and psychiatric outcomes in the active group. Such analyses will use post-randomization variables that are potential mediators –e.g., group and individual session visit and exercise class participation, specific pharmacotherapy use and adherence, and text-message self-monitoring activities.²²⁵ Even so, these analyses are more prone to biases because protection from confounding afforded by randomization is not likely applicable. Propensity score stratifications will be used to manage potential confounding in these analyses. Nevertheless, these findings will be interpreted with caution and will be considered exploratory.

Cost Analysis (Aim 4) will be conducted primarily from an adopting organization or payer's perspective (e.g., Medicaid) estimating incremental intervention implementation costs relative to control. Resource measurement will focus on sampling and tracking intervention staff time. We will sample at specified intervals for 1 week at a time. Tracking specific tasks will allow us to eliminate time spent strictly on research and perform sensitivity analyses with different potential levels of efficiency (e.g., amount of active client involvement vs. administrative time). We will use medication data and data on MD visits and hospitalizations to calculate cost per participant and total costs. With estimates of total costs, we will estimate incremental intervention costs and incremental costs per incremental improvement in 1° and 2° outcomes. To extend the time horizon forward, we will use the global FRS to project the proportion expected to have a CV event within 10 years and the present value of costs and QALYs associated with events, allowing us to perform a societal perspective cost-utility analysis.²²⁶ For all analyses, we will conduct univariate sensitivity analyses by varying assumptions and assess estimate uncertainty by bootstrapping for 10000 replications, drawing samples with replacement where samples have the same number of observations as the main study.²²⁷

Qualitative Analysis (Aims 5-6): Interviews will be transcribed and coded. NVivo will be used to enter and group discrete passages from data into themes. We will use the constant comparative method²²⁸ to categorize transcript statements that demonstrate common attributes, then combine categories into broader, recurrent themes using a hybrid approach where we will start with larger categories and then add nodes and subnodes as new concepts emerge until saturation of ideas is reached. Findings will be shared with study sites and the Advisory Committee to inform ongoing implementation and future sustainability and dissemination.

Power analyses: Under a conservative set of assumptions, this trial with sample size of 220 will have ≥80% power to detect a clinically meaningful effect in our primary outcome of 7-day point prevalence smoking abstinence at 18 months between intervention and control (Table 5). We assume:

1. Two-sided alpha =0.05.

2. Follow-up for primary outcome=100%. In smoking cessation trials, those lost to follow-up are classified as

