7. DATA COLLECTION AND MEASUREMENTS

Outcomes and Measures are collected at baseline, 6, 12, 15 and 18 months at mental health programs. Table 2 shows these measures.

Primary Outcome: The primary outcome will be 7-day point prevalence smoking abstinence at 18 months, defined as self-report of 7 days of not smoking, confirmed by expired CO <8ppm with a Bedfont Smokerlyzer II.^{175,181,182} Biochemical verification with available urine cotinine (if not on NRT) and/or anabasine will be used as needed to confirm self-reported abstinence, particularly if the validity of CO is expected to be low (e.g. COPD or difficulty forming an adequate seal on the smokerlyzer); and if CO is greater than 8 as this could be from second hand smoke or smoked cannabis.¹⁴⁸⁻¹⁵⁰

7-day smoking abstinence at 6, 12 and 15 mo. are secondary outcomes.

Other Secondary outcomes focus on AHA metrics for health risk behaviors¹⁶⁵ and include: a) continuous abstinence with 1) % continually abstinent over 3mo. (based on self-reports of abstinence since last visit, using timeline follow-back)¹⁸³, and biochemical verification at 15 and 18 month visits), 2) total days abstinent in the study with the same method; b) Weight and BMI; c) Physical fitness with 6-minute walk;¹⁸⁴⁻¹⁸⁶ and d) Healthy diet.¹⁸⁷ We will assess 10-year probability of a CVD event with the global Framingham Risk Score (FRS) incorporating smoking, total and HDL-cholesterol, systolic blood pressure and diabetes mellitus.¹⁸⁸ Others include: health status (SF-12)¹⁸⁹; Quality of life (Euroqol);¹⁹⁰⁻¹⁹² psychiatric symptoms (BPRS);¹⁹³ ED use and hospitalizations.

We will also examine the difference of mean CO change over time between intervention arms, and, among

Protocol: Trial of Integrated Smoking Cessation, Exercise and Weight Management in SMI

continuing cigarette smokers, change of mean number of cigarettes smoked per day over time between intervention arms.

Measurement methods: Measures for all participants are detailed below, and will be conducted using standardized procedures, and following quality control procedures as in ACHIEVE and Drs. [name]' trials.^{51,61,121,125} The data collection team will be certified in and experienced with measures, and monitored by the study coordinator. All measures are collected at baseline, 6, and 18 months. At 12 months and 15 months we collect contact information, medications, smoking information, weight and event surveillance.

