To assess social networks around smoking, we will use the personal network approach measurement (also called the 'egocentric' approach) to elucidate the network ties that surround a focal individual.¹⁷⁵⁻¹⁷⁹ In particular, we will ask each participant to identify the wide range of network members with whom individuals interact and measure the participant's understanding of the connections among those people. We will assess health literacy with the Health Literacy Skills Instrument. The sexual behaviors of persons with serious mental illness have implications for their emotional and physical well-being. These behaviors also affect the need for health care services that are focused on sexually transmitted diseases, family planning, and childbearing. Reproductive health will be measured with NHANES survey questions.¹⁸⁰ Health care access will be measured using adapted specific Behavioral Risk Factor Surveillance System Questions.¹⁸¹ Access to technology will be measured using adapted questions based on PEW Research Center.¹⁸²

Table 2. Data Collection Measures for All Participants	BL	6	12	15	18
Contact information	X	X	X	X	X
Demographics	X	X			X
Medical conditions	X	X			X
Substance Abuse	X	X	X	X	X
Medical history	X				X
Rose Angina	X				
Psychiatric diagnoses	X				
Medications	X	X	X	X	X
Physical measures					
Blood pressure	X	X			X
Weight	X	X	X	X	X
Height	X				
Waist circumference	X	X			X
6 minute fitness walk	X	X			X
Fasting blood measures	X				X
Urinary Cotinine and anabasine	X	X	X	X	X
Urinary Protein	X				X
Smokerlyzer CO	X	X	X	X	X
Instruments					
Healthy diet	X	X			X
Tobacco measures	X	X	X	X	X
Health status	X	X			X
Quality of Life	X	X			X
Neighborhood Questionnaire	X				X
Sleep habits	X				X
Medication Adherence	X	X	X	X	X
Psychiatric Symptoms	X	X			X
Physical Activity	X	X			X
Social Support					
Healthcare access questions	X				X
Technology	X				X
Reproductive health	X				X
Social Networks	X				X
Health Literacy	X				
Event Surveillance-safety	X	X	X	X	X

Event surveillance. We will identically apply a process to each randomized group and collect self-reported symptoms, health care utilization and records related to CVD and mental health outcomes, including ED use and hospitalizations, and use the SAFTEE¹⁸³ for possible medication side effects.

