Breach of confidentiality: All participant information will be considered confidential. This confidentiality will be assured through several mechanisms. Each participant will be assigned an anonymous study ID, which will be used on all study forms; all study forms and paper records that contain participant information will be kept in secured, locked areas when not in use. Such materials, when in use, will be kept away from public scrutiny. Forms that need to be discarded will be destroyed. Access to participant information will be restricted to authorized personnel. For computerized study data, access will be password protected. When the study database is ready for analysis, it will not contain identities of participants. During data collection, data collection forms will be stored in locked areas with access only by authorized personnel. Finally, neither the mental health programs nor participants will be identified by name in any publications. Data will not be presented in such a way that the identity of individual participants can be inferred.

Participant reimbursement: Participant reimbursement for data collection for all participants is estimated at \$115 total for completing all data collection visits, divided over each visit. Active intervention participants will receive small incentives for group and individual session attendance and for low smokelyzer readings. These will consist of earning points that may be traded in for small gifts, or earning up to \$3 for session attendance or smoking abstinence. A participant in the active intervention arm could earn up to \$200 over the course of the 18-month study for intervention participation.

Potential benefits of the proposed research to the subjects and others: Potential benefits to the study participants who receive intervention include improved health behaviors and improved cardiovascular risk profiles. All participants receive blood pressure and laboratory test results. Potential benefits to others include the possibility that the research will lead to the dissemination of effective interventions to decrease tobacco dependence and improve overall cardiovascular health in persons with serious mental illness.

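### The 18-month count of abstinent days borrows a verification rule that names the 15- and 18-month visits, so read literally it takes months 0 to 12 on self-report

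*Combined protocol and SAP*

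**What the plan says.** Section 13 lists two continuous-abstinence outcomes in one sentence. The first is the percentage continuously abstinent over 3 months, "based on self-reports of abstinence since last visit, using timeline follow-back", together with verification at two named visits. The second takes its derivation from the first: "biochemical verification at 15 and 18 month visits), 2) total days abstinent in the study with the same method". Section 7 has the same definition ("biochemical verification at 15 and 18 month visits), 2) total days abstinent in the study with the same method; b) Weight and BMI").

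Other parts of the plan that bear on this:

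- **Visits.** "Formal assessments are at baseline, 6, 12, 15 and 18 months" (Section 13).
- **Samples.** Table 2 in Section 7 marks both the CO reading and "Urinary Cotinine and anabasine" at baseline, 6, 12, 15 and 18 months.
- **Verified abstinence.** The primary outcome is "defined as self-report of 7 days of not smoking, confirmed by expired CO <8ppm with a Bedfont Smokerlyzer II". Urine cotinine (for those not on NRT) and/or anabasine is used where CO is doubtful or raised. Point-prevalence abstinence at 6, 12 and 15 months is secondary and is modelled jointly with the 18-month outcome.
- **Analysis of the day count.** The secondary analyses in Section 13 give it a linear mixed model with visit-by-intervention terms. They give no rule for deriving the days.
- **Blinding.** Under Section 9, participants and coaches know the assignment; data collectors are meant not to.

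**The concern.** A schedule that names the 15- and 18-month visits suits an outcome whose window is months 15 to 18. It does not suit a count that starts at randomisation. If the sentence is followed as written, the 6- and 12-month CO and urine results play no part in the day count, although they are collected.

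Two things are at stake. First, for most of follow-up the count would rest on what participants say about themselves while knowing their arm, in a trial that does not accept self-report alone for its main abstinence outcome. Second, the same days could be scored as smoking in one reported outcome and as abstinent in another, with no rule to reconcile them.

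**Working it through.** The plan states no figure for the share of days verified, so there is none to reproduce.

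**Inputs.** Visits at 6, 12, 15 and 18 months (Section 13) give intervals of 6, 6, 3 and 3 months. Verification for the day count is named at 15 and 18 months (Sections 7 and 13). The point-prevalence window is 7 days (Section 13). Days are converted at 30.4375 per month, so 18 months is 547.9 days, about 548.

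**Step 1: follow-up time with no named check.** Literal reading: (6 + 6) / (6 + 6 + 3 + 3) = 12/18 = 66.7%, or 12 × 30.4375 = about 365 of 548 days. With all four visits named, 0/18 = 0%.

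**Step 2: why this is not a share of counted days.** For someone who quits at month q (up to 12) and stays abstinent, the share of counted days falling before month 12 is (12 − q)/(18 − q).

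| Pattern | Share of counted days before month 12 |
|---|---|
| Quit at month 0, stay abstinent | 12/18 = 66.7% |
| Quit at month 3, stay abstinent | 9/15 = 60% |
| Quit at month 6, stay abstinent | 6/12 = 50% |
| Quit at month 9, stay abstinent | 3/9 = 33.3% |
| Quit at month 12 or later | 0% |
| Abstinent in months 2 to 12 only | 10/10 = 100% |

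The share depends on when abstinence falls, anywhere from 0% to 100%.

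**Step 3: direct conflict with point prevalence.** The windows at risk are the 7 days before the 6-month and the 12-month visits: 2 × 7 = 14 days per participant at most, and 14/548 = 2.6% of follow-up. This assumes that the CO criterion applies at 6 and 12 months. The plan does not restate it there, but model (1) defines its response at those visits as the binary primary outcome.

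**Step 4: one record under each rule.** Take a hypothetical participant who reports the last 60 days as smoke-free at the 6-month visit, with CO of 20 ppm and a positive urine test. Point prevalence at 6 months scores smoking.

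| Rule for the day count | Days credited from this run |
|---|---|
| Literal current text | 60 |
| Failed test cancels the 7-day window | 60 − 7 = 53 |
| Failed test cancels the whole claimed run | 60 − 60 = 0 |

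The first row contradicts the point-prevalence result. The other two agree with it and differ only in how far back a failed test reaches, which the plan does not say.

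**The case against.** **The text does not say that only those two visits count.** The same method may mean follow-back plus verification in general, applied at whatever visits fall in the window. The 15- and 18-month visits may be named simply because they bound the first outcome. Section 7 also says that urine markers will be obtained as appropriate to confirm smoking status. This stands: the exclusion of the 6- and 12-month tests is an inference from the literal wording. But the milder reading still leaves open how many reported days a failed test cancels, so two analysts could derive different totals from one record.

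**Any follow-back count is mostly self-report.** If a test vouches only for its own 7 days, self-report alone covers (548 − 14)/548 = 97.4% of days with two tested visits and (548 − 28)/548 = 94.9% with four. This also stands. The gain from the change is consistency between outcomes and use of results already collected, not verification of every day.

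**A reader might infer that the active arm is paid to over-report.** Section 17 mentions earnings "for session attendance or smoking abstinence". But the sentence before it there refers to low Smokerlyzer readings, and the reinforcement paragraph in Section 10 ties the abstinence reward to biochemical confirmation. An unverified claim earns nothing. Blinded data collectors, and weekly CO readings during the active cessation phase, may also discourage false claims. What remains is that participants know their arm.

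**A reader might also want a percentage inflation of the arm difference.** That would need an excess misreporting rate and a typical length of falsely claimed run; the documents give neither. Multiplying the planned 18-month difference in abstinence rates by the days of follow-up does not give an upper bound for the true difference, because abstinence may be commoner earlier. Section 3 reports 43% abstinent at week 12 and 28% of the original sample at one year in a previous trial.

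**Conclusion.** The concern holds in a limited form. Read literally, the day count has no named biochemical check for the intervals closed by the 6- and 12-month visits: 12 of 18 months, two thirds of follow-up time. It can credit up to 14 days per participant that the point-prevalence outcome and model (1) score as smoking, together with the rest of the claimed run ending at the failed visit.

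This rests on the literal reading of the shared-method wording and on the CO rule applying to point prevalence at 6 and 12 months. The documents do not support a statement about the size or direction of bias in the arm comparison. The effect is confined to one secondary outcome. The primary outcome, its model and its power are untouched. The change is worth making because the samples are already scheduled.

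**What to change.** In Sections 7 and 13, replace the shared-method wording for total days abstinent with a definition of its own:

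- timeline follow-back days since the last visit, with biochemical verification at the 6-, 12-, 15- and 18-month visits under the primary-outcome rule;
- when verification fails, at least the 7 days before that visit are scored as smoking, so that the count agrees with point prevalence.

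Report two sensitivity analyses: (a) the whole claimed abstinent run ending at the failed visit scored as smoking, and (b) the self-report-only total. Whole-run cancellation belongs in a sensitivity analysis because one failed test after a recent lapse could erase up to six months of genuine abstinence. The same sentence should say how a missing test is handled.

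The cost is a sentence in each section and a few lines of code, with no new visit, sample or participant. There is a small downside: some truly abstinent days may be lost when CO is raised for other reasons. The urine check limits this, but its cotinine part cannot be used for participants on NRT, which is a component of the active intervention. The plan places no such limit on anabasine.

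### Does the plan's no-bias statement under MAR fail for the GEE analysis of abstinence, and is its MNAR imputation too loosely specified to run?

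*Combined protocol and SAP*

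**What the plan says.** All of this is in section 13, Data Analysis.

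- **Core analytic model.** Abstinence at the follow-up visits is modelled by logistic GEE with an unstructured working correlation. A random-effects model is considered and set aside for reasons of interpretation: "we will estimate our primary mean model through the GEE approach in GenMod with resultant estimates representing population average odds ratios". Weights are not mentioned. A first-order transition model is offered as an adjunct: "Although model (1) will support our principal analyses, there is an attractive, transition model alternative".
- **Missing data.** The team expects little loss: "we anticipate less than 10% of follow-up data will be missing". Participants with missing smoking data are first counted as smokers. A MAR analysis comes second, with no separate model named for it, and the reason given for trusting it is that "estimates based on an appropriate analytic model (both the mean and error structure) for the observed data will not be biased". Because MAR cannot be tested, a sensitivity analysis follows, by "multiple imputation using a model derived from our analytical model under MAR, maintaining the covariance structure and modifying the imputation mean" to represent informative dropout. The scenarios are not listed.
- **Secondary analyses.** Continuous outcomes use "linear mixed models employing visit by intervention interaction terms in the mean model and unstructured correlation in the covariance model". Covariates linked to the "presence of missing data will be included in the mean model as appropriate", and patients are to be grouped by missingness pattern to guide modelling and sensitivity analyses.
- **Power analyses.** Follow-up is taken as 100% because losses count as smokers.

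**The concern.** Under MAR, the missingness process can be ignored when inference rests on a correctly specified likelihood. The linear mixed models for the continuous outcomes meet that condition. GEE does not: its correlation is a working assumption, and its estimating equations from incomplete data need not centre on the truth when dropout depends on earlier outcomes. Since GEE is the only model the plan commits to for abstinence, the no-bias sentence seems to credit the primary endpoint's MAR analysis with a property its method lacks.

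The MNAR rule also reads like one for normal data. For a binary outcome the variance p(1-p) moves with the mean, so one cannot be changed while the other is held, and GEE supplies no joint distribution from which to impute. With no scale, shift sizes or arm rule, two analysts could report different robustness results.

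At stake would be a biased MAR odds ratio for the primary endpoint, and a sensitivity analysis whose settings could be chosen after seeing the data.

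**Working it through.** **Inputs from the plan.** 220 participants in equal allocation, so 110 per arm; control abstinence 3-5%; intervention abstinence 17.5-21.5%; four follow-up visits; under 10% missing. The plan states no bias figure to reproduce. As a check on the inputs, exact Fisher power at 110 per arm for 5% versus 17.5% is 0.81, against 0.80 in Table 5 (17.5% being the average of 25% and 10%).

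**Assumptions not in the plan.** Constant abstinence of 19% and 5%; a first-order Markov outcome with stated persistence of abstinence between visits; monotone dropout per visit of 2.7% among previous smokers and 0.7% among previous abstainers, everyone being a smoker at baseline.

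**Step 1: scale.** True OR = (0.19/0.81)/(0.05/0.95) = 4.46. SE of the log OR = sqrt(1/(110×0.19×0.81) + 1/(110×0.05×0.95)) = 0.500.

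**Step 2: missing at 18 months.** Intervention: the average hazard after the first visit is about 0.81×2.7% + 0.19×0.7% = 2.32%, so 1 - 0.973×0.9768³ = 9.3%. Control: 0.95×2.7% + 0.05×0.7% = 2.60%, so 1 - 0.973×0.974³ = 10.1%.

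**Step 3: large-sample GEE bias.** Solving the population GEE equations (visit-by-arm mean, pooled unstructured correlation) gives:

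| Persistence, intervention/control | Log-OR bias | Bias/SE |
|---|---|---|
| 0.9/0.5 | +0.029 | +0.06 |
| 0.8/0.7 | +0.006 | +0.01 |
| 0.7/0.7 | -0.004 | -0.01 |
| 0.7/0.8 | -0.013 | -0.03 |
| 0.5/0.9 | -0.034 | -0.07 |

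The extremes are 4.46×exp(-0.034) = 4.31 and 4.46×exp(+0.029) = 4.59. With random-intercept instead of Markov data, the bias is -0.013 to +0.022.

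The 0.7/0.7 row can be seen by hand from simple observed proportions. Abstinence among the missing is 15.0% and 3.7%, so the observed rates are (0.19 - 0.093×0.150)/0.907 = 0.1941 and (0.05 - 0.101×0.037)/0.899 = 0.0515. Their OR is about 4.44, a log difference of about -0.004. Both arms lose mainly smokers, so the distortions largely cancel.

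**Step 4: other dropout patterns.** A separate calculation at 5% versus 17.5% (true OR 4.03) and about 10% missing gave ORs of 4.00 to 4.12. Over the rates examined, including 3% versus 21%, the log-OR bias was -0.011 to +0.029. The upper end came from control abstainers and intervention smokers dropping out.

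**Step 5: would weighting help?** With a correct weight model, weighted GEE has zero large-sample bias. In simulations of 6,000 trials per case (Monte Carlo SE 0.002), the mean differences from the full-data log OR were:

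| Case | GEE | Weighted GEE |
|---|---|---|
| Markov 0.9/0.5 | +0.037 | +0.006 |
| Markov 0.5/0.9 | -0.029 | +0.003 |
| Markov 0.7/0.7 | +0.004 | +0.006 |
| Random intercept SD 4/1.5 | +0.034 | +0.011 |
| Random intercept SD 1.5/4 | -0.000 | +0.010 |
| Random intercept SD 3/3 | +0.016 | +0.008 |

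Weighting is nearer in four cases and no nearer in two. In the Markov cases the empirical SE falls only from 0.578, 0.569 and 0.582 to 0.573, 0.566 and 0.579. The weight model is also sparse: 5.5 control abstainers over three transitions at 0.7% gives 16.5×0.007 = 0.12 expected dropouts, and 0.993^16.5 = 89% of trials would have none.

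**Step 6: MNAR shifts on the log-odds scale** (persistence 0.7/0.7, true OR 4.46):

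| Shift | Both arms | Intervention only | Control only |
|---|---|---|---|
| -0.7 | 4.44 | 4.24 | 4.66 |
| -1.4 | 4.42 | 4.14 | 4.76 |

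Missing as smoking gives 4.40. The full range, 4.14 to 4.76, is -0.073 to +0.065 in log OR, or -0.15 to +0.13 SE.

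**The case for a change.** The strongest case for acting is that the mismatch is real. With the mean model exactly right and the planned unstructured correlation in place, some bias remains, and the plan names no other model for the binary MAR analysis. The covariate provision sits under the secondary analyses and does not by itself deal with dropout driven by earlier smoking status. Beyond the plan's missingness the bias grows: -0.074 to +0.064 at 18.5-20.0% missing, and +0.06 to +0.20 when 20-30% is missing with strongly opposite dropout in the two arms.

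The MNAR settings matter too. At 10% missing and a true OR of 4.03, a shift of -1 logit in both arms gives 4.01, while -5 percentage points in both gives 4.35, the opposite direction. Counting only the missing intervention participants as smokers gives 3.55 and takes power from 0.84 to 0.75 (pooled formula). Also imputing missing controls at 17.5% gives 2.80 and power 0.62. Stating these settings in advance would cost little, since imputation is already planned.

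What stands is that the sentence is exact for likelihood models and only approximate for GEE, and that the MNAR details are unwritten. What does not stand is that this harms the trial. The larger biases need missingness well above what the plan expects; section 6 reports 99% outcome data in the team's previous trial. The percentage-point shift is not a serious competitor for a logistic model: at 3% control abstinence it implies an imputed rate of -2%. The ORs of 3.55 and 2.80 come from deliberately one-sided or opposed scenarios, and spread across scenarios is what a sensitivity analysis is meant to show.

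**Conclusion.** No change to the plan follows. On the MAR statement there is no material gain to be had: the sentence is conditional, and at the expected missingness unweighted GEE misses the truth by at most about 0.03 in log OR, or 0.07 SE, in either direction. Weighting would exchange that for dependence on a sparse weight model and loss of the prespecified unstructured correlation, without a consistent improvement.

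On MNAR this is missing detail that an analyst can fill sensibly. An imputation model derived from a logistic analysis points to log-odds shifts. Keeping the covariance structure can be read as leaving the dependence on previous status unchanged, and the transition model already described provides the distribution to draw from. Run at zero shift, the same imputation gives a MAR result that does not lean on GEE. Reporting the shifts in both arms and in each arm alone covers the arm question.

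The conclusion rests on missingness near or below 10%, on dropout linked to previous smoking status as assumed above, and on the plan's abstinence rates. It would need another look if losses reached 20-30% with opposite patterns by arm. The missing-as-smoking analysis, the sample size and the power figures do not depend on either point.
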